17.1. Primary Effectiveness Endpoints

Benign Pigmented Lesions

Mean difference from Baseline to final 12-Week follow-up visit in Pigment Clearance Score as determined by blinded evaluators from clinical photographs.

Wrinkles

Mean difference from Baseline to final 12-Week follow-up in Fitzpatrick Wrinkle Score as determined by blinded evaluators from clinical photographs.

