	
 10. Severe immunosuppression resulting from medications and/or a medical condition that could impair healing after treatment. 11. Open wound or infection in the intended treatment area 12. History of light induced seizure disorders 13. Dermatologic and/or cosmetic procedures in the intended treatment area(s) during the past six months 14. The subject is not suitable, in the opinion of the clinician, for participation in the study due to medical or other reasons that could compromise the study integrity or subject safety
Study Visit Outline	
NOTE: Screening Visit and Baseline/Treatment Visit #1 may occur on the same day
 
Screening Visit:
 
 1. Informed Consent 2. Inclusion and Exclusion Criteria Review 3. Medical History Review 4. Concomitant Medication Review 5. Fitzpatrick Skin Type (FST) Evaluation 6. Benign Pigmented Lesion and Wrinkle Evaluation 
Baseline / Treatment Visit #1:
 
 1. Clinical Photography 2. Laser Treatment 3. Local Skin Response Assessment 4. Subject Pain Score Assessment 5. Safety Assessment 6. Skin Biopsy (optional) 
Telephone Contact
 
 1. 10 days +/- 7 days after each treatment 
Treatment Visits #2 to #4:
 
 1. Clinical Photography 2. Subject Satisfaction Score 3. Laser Treatment 4. Local Skin Response Assessment 5. Subject Pain Score Assessment 6. Safety Assessment 7. Skin Biopsy (optional) 
Follow-Up Visits: 4 ± 1 week, 8 ± 2 weeks, 12 ± 4 weeks.
 
 1. Clinical Photography 2. Subject Satisfaction Score 3. Local Skin Response Assessment 4. Safety Assessment 5. Skin Biopsy (optional)
Measurement Instruments	
5-Point Pigment Clearance Scale (Appendix A)
 
9-Point Fitzpatrick Wrinkle Scale (Appendix B)

	
11-Point Subject Pain Scale (Appendix C)
 
5-Point Subject Satisfaction Scale (Appendix D)
 
Local Skin Response (Appendix E)

Primary Efficacy Endpoints	
1. Benign Pigmented Lesions Mean difference from Baseline to 12-week follow-up in Pigment Clearance Score (PCS) as determined by blinded evaluators from clinical photography
 
2. Wrinkles Mean difference from Baseline to 12-week follow-Up in Fitzpatrick Wrinkle Score (FWS) as determined by blinded evaluators from clinical photography

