Secondary Efficacy Endpoints	
1. Benign Pigmented Lesions Percentage of subjects demonstrating Pigment Clearance Score (PCS) of 3 or 4 (> 50% improvement) comparing Baseline to 12-week follow-up as determined by blinded evaluators from clinical photographs
 
2. Wrinkles Percentage of subjects demonstrating ≥ 1 score improvement in Fitzpatrick Wrinkle Score (FWS) from Baseline to 12-week follow-up visit as determined by agreement of 2 out of 3 blinded evaluators from clinical photographs
 
3. Subject Satisfaction Mean and distribution of Subject Satisfaction Scores at all visits beyond Treatment Visit #1
 
4. Subject Pain Mean and distribution of Subject Pain Scores following each treatment

Primary Safety Endpoint	Incidence, severity and relatedness of adverse device effects based on total number of laser treatments performed
Exploratory Endpoint	Analysis of laser-tissue effects and/or healing response from pre- and post-treatment skin biopsies using light microscopy and/or scanning electron microscopy

2. Abbreviations

ADE	Adverse Device Effect
cm, cm²	Centimeter, Square Centimeters
CFR	Code of Federal Regulations
Ø	Diameter
FDA	Food and Drug Administration
FST	Fitzpatrick Skin Type
FWS	Fitzpatrick Wrinkle Score
GCP	Good Clinical Practice
Hz	Hertz
IEC	Independent Ethics Committee
IRB	Institutional Review Board
J	Joule
µbeam	Microbeam
µm	Micron
µs	Microsecond
mJ	Millijoule
mm	Millimeter
ms	Millisecond
nm	Nanometer
Nd:YAG	Neodymium: Yttrium Aluminum Garnet (YAG)
NSR	Non-Significant Risk
PCS	Pigment Clearance Score
PSS	Pigment Severity Score
ps	Picosecond
SE	Side Effect
SOP	Standard Operating Procedure
Tx	Treatment
UADE	Unanticipated Adverse Device Effect

3. Study Objective

The purpose of this study is to evaluate the PicoWay® Laser System with 730 nm handpiece and Resolve™ Fusion 1064 nm and 532 nm fractional handpieces for the treatment for benign pigmented lesions including dyschromia, and wrinkles including fine lines.

4. Background

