17.3. Secondary Endpoints

1. Benign Pigmented Lesions

Percentage of subjects demonstrating Pigment Clearance Score (PCS) of 3 or 4 (> 50% improvement) comparing baseline to 12-week follow-up as determined by blinded physician evaluators from clinical photographs

2. Wrinkles

Percentage of subjects demonstrating ≥ 1 score improvement in Fitzpatrick Wrinkle Score (FWS) from baseline to 12-week follow-up visit as determined by agreement of 2 out of 3 blinded physician evaluators from clinical photographs

3. Subject Satisfaction

Mean and distribution of Subject Satisfaction Scores at all visits beyond Treatment Visit #1

4. Subject Pain

Mean and distribution of Subject Pain Scores following each treatment

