19.2. Hypotheses

Null and alternative hypotheses are stratum specific. They assess the change from Baseline to Week 12/study exit.

Pigment effectiveness (5-point ordinal scale, 5 is best) will be evaluated according to the following null and alternative hypotheses for Group A:

- Null Hypothesis: Less than 50% experience good to excellent improvement in the Pigment Clearance Score (PCS)
- Alternative Hypothesis: At least 80% experience good to excellent improvement in PIS.

Fitzpatrick Wrinkle Score (9-point ordinal scale, 1 is best) will be evaluated separately for peri-orbital wrinkles and peri-oral wrinkles as well as the sum according to the following null and alternative hypotheses for Group B:

- Null Hypothesis: There is no mean improvement in the Fitzpatrick Wrinkle Score (FWS)
- Alternative Hypothesis: There is at least a 2-point mean improvement in FWS.

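### Group A is listed with a mean Pigment Clearance Score as primary endpoint but is hypothesised and powered on a responder proportion listed as secondary, and section 19.4 reverses the pigment and wrinkle tests

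*Combined protocol and SAP*

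**What the plan says.** **Listed endpoints.** Section 17.1 gives the Group A primary endpoint as the "Mean difference from Baseline to final 12-Week follow-up visit in Pigment Clearance Score", scored by blinded evaluators from photographs. The synopsis says the same. The responder endpoint, "Percentage of subjects demonstrating Pigment Clearance Score (PCS) of 3 or 4", is listed as secondary in both the synopsis and 17.3.

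**Hypotheses and sizing.** Section 19.2 states the Group A hypotheses only as a responder proportion. The null is a rate below 50%; the other side reads "Alternative Hypothesis: At least 80% experience good to excellent improvement in PIS". Section 19.3 says that its sizing is for each group's primary efficacy endpoint. For Group A it sizes that proportion: 50% against 75%, two-sided exact binomial test at 5%, 30 evaluable subjects, 80% power. For Group B it sizes a 1-point mean improvement in the Fitzpatrick Wrinkle Score (FWS) by a two-sided paired t-test, with 34 evaluable subjects and a 2-point SD.

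**Tests.** Section 19.4 assigns the paired t-test, on peri-orbital, peri-oral and combined outcomes, to the skin pigmentation score. It assigns the two-sided exact binomial test to wrinkle improvement. Yet 19.2 says of FWS that it "will be evaluated separately for peri-orbital wrinkles and peri-oral wrinkles as well as the sum".

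**The scale.** Section 9.1 describes PCS as a grade of improvement coded 0 to 4. Appendix A codes it 1 to 5, with 5 for complete response.

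**The concern.** The 80% power claimed for Group A belongs to an endpoint listed as secondary. The endpoint listed as primary has no hypothesis, margin, SD or power anywhere in the document.

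The listed endpoint is also poorly defined. Under 9.1, section 18 and Appendix A, PCS already rates improvement relative to Baseline, from pairs of photographs. A subject therefore has no Baseline PCS to subtract, and no reference value is named.

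Followed literally, 19.4 would analyse pigment by facial regions that 19.2 assigns to wrinkles, although section 7 allows pigmented lesions on the scalp, back, hands or feet. Wrinkles would get a binomial test for which no null proportion is stated. With two candidate primary results for Group A, the one that counts could be chosen after the data are seen.

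**Working it through.** **1. Reproduce the Group A size.** Inputs from 19.3: n=30, p0=0.50, p1=0.75, two-sided 5%, exact binomial. The upper critical value is the smallest r with P(X ≥ r | n, 0.50) ≤ 0.025.

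| Result | One-sided tail at 50% | Two-sided p | Exact 95% CI |
|---|---|---|---|
| 20/30 = 66.7% | 0.0494 | 0.099 | 47.2% to 82.7% |
| 21/30 = 70.0% | 0.0214 | 0.043 | 50.6% to 85.3% |

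So r=21. Power is P(X ≥ 21 | 30, p1): 80.3% at 75% (the 19.3 value) and 93.9% at 80% (the 19.2 value). At 75%, n=28 gives 75.0% and n=29 gives 71.3%; 30 is the smallest n that reaches 80%. The plan's figure is reproduced. Its own significance threshold is redacted, so 21/30 is a calculated value.

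**2. Reproduce the Group B size.** Inputs from 19.3: difference 1, SD 2, two-sided 5%, paired t-test. Power comes from the noncentral t distribution with n−1 degrees of freedom and noncentrality (difference/SD)×√n.

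- n=34: noncentrality (1/2)×√34 = 2.92, power 80.8%.
- n=33: noncentrality (1/2)×√33 = 2.87, power 79.5%.

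So 34 is the smallest n that reaches 80%.

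**3. Compare with 19.4.** Both sizes are the minimum for binomial with 30 and t-test with 34, which 19.3 ties to pigment and wrinkles respectively. Exchanging the two sizes misses 80% in both: the t-test at n=30 has 75.4% power, and the binomial at n=34 (50% against 75%) has 78.9%.

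| Item | 19.2 and 19.3 | 19.4 |
|---|---|---|
| Exact binomial test | Pigment | Wrinkles |
| Paired t-test | Wrinkles | Pigment |
| Peri-orbital and peri-oral regions | Wrinkles | Pigment |

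The 19.4 sentence on a 1-point improvement, placed after the pigment t-test, matches the wrinkle secondary endpoint in 17.3, which concerns "score improvement in Fitzpatrick Wrinkle Score (FWS) from baseline to 12-week follow-up visit". The labels therefore appear to be swapped. Undoing the swap gives pigment the binomial test and leaves mean PCS without a test.

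**4. Power for the listed primary endpoint.** This cannot be computed, because no PCS difference or SD is given.

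**5. Can the two endpoints disagree?** An illustration, assuming Appendix A coding with the lowest grade as reference: 15 subjects at grade 3 and 15 at grade 1.

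- Mean change = (15×2 + 15×0)/30 = 1.0; SD = √(30/29) = 1.02; t = 1.0/(1.02/√30) ≈ 5.4, p<0.001.
- Responders = 15/30 = 50%, exact binomial p=1.0.

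The same data succeed on a mean-change test and fail the hypothesis in 19.2.

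**The case against.** The strongest reply is that the plan is not silent. Section 19.3 ties its sizing to the primary endpoints and gives a test, alpha, null and alternative for Group A, so the intended primary can be inferred. That is fair as a guide to intent, but the synopsis and 17.1 say otherwise in plain terms, and an inference does not reorder listed endpoints.

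A second reply is that 19.4 as written does give the pigment score a paired t-test, which would suit a mean difference. The region labels and 19.3 rule this out as the likely meaning. It remains true that the listed endpoint lacks a test only after the labels are corrected.

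A third is that section 19.1 promises a SAP before study initiation. A SAP could correct the 19.4 labels, but the order of primary and secondary endpoints is set in the protocol.

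A fourth is that the sponsor could keep mean PCS as primary. That would be coherent, but it needs a defined reference, a margin, an SD and new sizing. The responder endpoint already has its hypothesis, test and n.

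Some side points stand as separate gaps that this change neither creates nor worsens:

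- PCS has no rule for combining three evaluators' scores.
- Exact binomial power is not monotone in n (77.1% at 31 and 73.7% at 32, for a 75% rate).
- No SD is given for the sum of the two wrinkle regions.
- The Group B alternative is 2 points in 19.2 but 1 point in 19.3.

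**Conclusion.** The concern holds and must be fixed. The Group A endpoint listed as primary is not the one hypothesised and powered, and 19.4 assigns the two tests to the wrong groups when read against 19.2 and 19.3. The endpoint-type mismatch is confined to Group A: the listed Group B primary, a mean FWS difference, agrees in type with its hypothesis and sizing.

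The sample-size arithmetic is sound. The stated 80% (80.3% calculated) belongs to the responder proportion; the listed mean PCS difference has no stated power. That 19.4 is a label swap is an inference, though a strong one. The endpoint conflict does not depend on it.

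**What to change.** 1. **Synopsis and 17.1:** make the Group A primary endpoint the proportion of subjects with at least 50% clearance at the 12-week follow-up, tested against 50% by the two-sided exact binomial test at 5%.
2. **Synopsis and 17.3:** list mean PCS at Week 12 as a descriptive secondary summary in place of the responder item.
3. **Section 19.4:** assign the exact binomial test to Group A. Assign to FWS in Group B both the paired t-test by region and the sentence on the percentage with a 1-point improvement.
4. **Synopsis, 9.1, 17.3, 19.2 and Appendix A:** use one PCS coding, and define response by percent clearance. Under Appendix A coding, a response defined as grade 3 or 4 leaves out the complete responders at grade 5.
5. **Minor:** align the 80% alternative in 19.2 with the 75% used in 19.3.

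The cost is a protocol edit to those sections before any photographs are scored. No new data are needed, and n=30 and n=34 stand.

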17.2. Primary Safety Endpoint

Analysis of the incidence, severity and relatedness of local skin responses and anticipated adverse device effects (ADE) and unanticipated adverse device effects (UADE).

17.3. Secondary Endpoints

1. Benign Pigmented Lesions

Percentage of subjects demonstrating Pigment Clearance Score (PCS) of 3 or 4 (> 50% improvement) comparing baseline to 12-week follow-up as determined by blinded physician evaluators from clinical photographs

2. Wrinkles

Percentage of subjects demonstrating ≥ 1 score improvement in Fitzpatrick Wrinkle Score (FWS) from baseline to 12-week follow-up visit as determined by agreement of 2 out of 3 blinded physician evaluators from clinical photographs

3. Subject Satisfaction

Mean and distribution of Subject Satisfaction Scores at all visits beyond Treatment Visit #1

4. Subject Pain

Mean and distribution of Subject Pain Scores following each treatment

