9.1. Pigment Clearance Score (PCS)

Clearance of pigment following study treatment will be measured using a validated 5-point Pigment Clearance Scale (PCS) that categorizes improvement in the appearance of pigmented lesions from 0=0% or No Improvement to 4=75-100% or Excellent Improvement.¹⁴ The PCS scoring scale is provided in Appendix A.

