19.1. Statistical Plan Overview

The study will be conducted with two separate strata (pigment, wrinkles) which will be evaluated. Benign pigmented lesions including dyschromia (Group A) and wrinkles including fine lines (Group B) will be separately powered and analyzed for efficacy and safety while both groups will further be combined for safety analyses. All study sites will be eligible to enroll subjects into each stratum; no subject will be enrolled into both strata.

Subjects participating in the pigment treatment stratum will be evaluated using the Pigment Clearance Score (Appendix A) while subjects participating in the wrinkle treatment stratum will be evaluated using the Fitzpatrick Wrinkle Score (Appendix B). All study subjects will also be evaluated using the Subject Pain Scale (Appendix C), Subject Satisfaction Survey (Appendix D), the Local Skin Response (Appendix E), and will be evaluated for safety according to 21 CFR Part 812 as well as ICH guidelines (E3 and E6) and ISO 14385:2016 as applicable.

A statistical analysis plan (SAP) will be finalized prior to study initiation. The database will be constructed using Microsoft Office Excel (Microsoft, Redmond, WA). The database will be locked following a review of all protocol deviations to be classified as a major or minor deviation. Major and minor protocol deviations will be reviewed once all data undergo source document verification and prior to database lock. The independent biostatistician will determine major vs. minor protocol deviations.

Data analyses will be performed using SAS Version 9.3 or later (SAS Institute, Cary NC) and StatXact Version 10 or later (StatXact, Cambridge MA). All analyses will be performed in a GCP environment controlled by SOPs.

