30.1. Appendix A: Pigment Clearance Score Pigment Score

Score	Clearance	Description
1	0% - 24%	Poor response
2	25 - 49%	Fair Response
3	50 - 74%	Good response
4	75 - 94%	Excellent response
5	$\geq 95\%$	Complete response

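### The Pigment Clearance Score is 0–4 in Section 9.1 but 1–5 in Appendix A; on Appendix A the 3-or-4 responder rule leaves out complete responders

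*Combined protocol and SAP*

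**What the plan says.** Two codings of one instrument appear in the combined protocol and SAP.

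- **Section 9.1** describes a five-point score running "from 0=0% or No Improvement to 4=75-100% or Excellent Improvement", and then states: "The PCS scoring scale is provided in Appendix A".
- **Appendix A (Section 30.1)** scores 1 to 5: 1 = 0–24% (poor), 2 = 25–49% (fair), 3 = 50–74% (good), 4 = 75–94% (excellent), 5 = at least 95% ("Complete response").
- **Section 19.1** ties the analysis to the appendix: "Subjects participating in the pigment treatment stratum will be evaluated using the Pigment Clearance Score (Appendix A").
- **Section 19.2** agrees with the appendix on the top score: "Pigment effectiveness (5-point ordinal scale, 5 is best"). Section 19.3 also reports its planning data in Grades 3, 4 and 5.
- **Section 17.3 and the synopsis** define the responder endpoint as "Percentage of subjects demonstrating Pigment Clearance Score (PCS) of 3 or 4 (> 50% improvement").
- **Section 19.2** states the Group A null as "Less than 50% experience good to excellent improvement in the Pigment Clearance Score (PCS") and the alternative as "At least 80% experience good to excellent improvement in PIS". The score is PCS in the first and PIS in the second; the list of appendices in Section 30 also uses PIS.

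**The concern.** The responder rule was evidently written for the 0–4 scale, where 4 is the top grade and takes in everything from 75% to 100%. The scale attached to the protocol, and used in the statistical sections, has a further grade above 4. Read literally on that scale, the rule counts the best possible outcome as a failure, and the number (3 or 4) disagrees with the gloss beside it (more than 50% improvement). The good-to-excellent wording in both Section 19.2 hypotheses has the same gap, because Appendix A labels complete response as a separate grade above excellent.

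The same photographs can therefore give different endpoint values depending on which text is followed. The responder rate is at stake, and so is the mean PCS named as the primary pigment endpoint in Section 17.1, since 0% clearance scores 0 under Section 9.1 and 1 under Appendix A. If the choice is left until scores have been seen, the responder definition becomes post hoc.

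**Working it through.** **1. The rule on each scale.** Section 9.1 prints only its end grades. Its grades 1–3 are assumed here to be 1–24%, 25–49% and 50–74%.

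| Clearance | Section 9.1 score | Appendix A score | Meets the >50% gloss | 3-or-4 on 9.1 | 3-or-4 on Appendix A |
|---|---|---|---|---|---|
| 0% | 0 | 1 | no | no | no |
| 1–24% | 1 (assumed) | 1 | no | no | no |
| 25–49% | 2 (assumed) | 2 | no | no | no |
| 50–74% | 3 (assumed) | 3 | yes, except exactly 50% | yes | yes |
| 75–94% | 4 | 4 | yes | yes | yes |
| 95–100% | 4 | 5 | yes | yes | **no** |

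The last row is the conflict.

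**2. The plan's own power figure.** Inputs from Section 19.3: n = 30, null rate 50%, alternative 75%, two-sided exact binomial test at 5%.

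- P(X ≥ 21 | 30, 0.50) = 0.0214, doubled 0.0428, so 21/30 rejects.
- 20/30 gives a doubled tail of 0.0987 and does not reject.
- Power = P(X ≥ 21 | 30, 0.75) = 0.8034.

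The stated 80% holds, and it still holds with response defined as scores 3 to 5.

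**3. Loss at the planning figures.** Section 19.3 gives 30.8% at Grade 3, 53.8% at Grade 4 and 0% at Grade 5.

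- Scores 3–4: 30.8% + 53.8% = 84.6%.
- Scores 3–5: 30.8% + 53.8% + 0% = 84.6%.
- Loss: 0.

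**4. Loss per complete responder.** With one integer score per subject, the rate falls by (number at score 5)/30. For 1, 2 or 3 subjects that is 3.3, 6.7 or 10.0 percentage points.

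**5. Three evaluators.** Section 18 has three clinicians scoring independently. Section 17.3 gives a two-of-three rule for wrinkles but none for pigment. Suppose, as an assumption, that the wrinkle rule were used for pigment. Of the 5³ = 125 ordered rating triples:

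- At least two ratings of 3 or more: 3 × (3² × 2) + 3³ = 54 + 27 = 81.
- At least two ratings of 3 or 4: 3 × (2² × 3) + 2³ = 36 + 8 = 44.
- Lost: 81 − 44 = 37. Of these, 3 × 4 + 1 = 13 have at least two 5s (median 5). The other 6 × 2 × 2 = 24 have one 5, one rating of 3–4 and one of 1–2 (median 3 or 4; for example 5/4/2).
- Triples that pass 3-or-4 but fail 3-or-more: 0.

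These are counts of patterns, not probabilities. They show only that the loss need not equal the share at score 5 and that it always runs downwards.

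**6. Mean score.** From the table, the two codings differ by 1 at exactly 0% clearance and by 1 at 95% or more. So the Appendix A mean minus the Section 9.1 mean equals the share at 0% plus the share at 95% or more. At the planning figures the share below 50% is 100% − 84.6% = 15.4% and the complete share is 0%, so the shift lies between 0 and 0.15 points. The upper end needs every subject below 50% to show no clearance at all.

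**The case against.** The conflict between the scales is not in dispute; the objections concern its weight.

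- **No documented effect.** The only complete-response share in the document is 0%, and there the two readings agree. This stands. But that figure comes from a cited study and does not predict this trial, and Section 21.2 itself lists complete clearance as a possible benefit.
- **The intent is readable.** The gloss shows that 95% clearance was meant to count, and Appendix A scores can be regrouped as 3 or more without re-reading photographs. This probably states the intent correctly. It does not remove the defect: a programmer who codes the printed scores gets a different rate from one who codes the gloss.
- **The error is conservative.** The literal rule can only understate response, so it cannot create a false success. This also stands. A biased secondary estimate still needs correcting.
- **Good to excellent may mean good or better.** That is a fair reading, and Section 19.3 lists all three upper grades before it speaks of an improvement rate. The Section 19.2 wording is a looser form of the gap than the numeric rule, but on the appendix labels it does not name the complete grade.
- **If Section 19.2 has the gap, power should suffer.** It would only under the literal reading and a non-zero complete share. Section 19.3 states power for an improvement rate without adopting the 3-or-4 rule, and Section 19.4 assigns the pigmentation score a paired t-test. No power loss is claimed.
- **Support for Appendix A is thinner than it looks.** Section 19.1 only points to the appendix, as Section 9.1 does, and the Section 19.3 grades describe another study. Section 19.2 is the one independent statement of a top score of 5. It is still enough to show that the statistical text was written on the 1–5 scale.

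**Conclusion.** The point holds. Section 9.1 and Appendix A give different scales for the same score, no text reconciles them, and the 3-or-4 rule is right on the first and wrong on the second. On Appendix A scores it omits subjects with at least 95% clearance and contradicts its own gloss.

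The size is nil at the planning distribution. Otherwise it is 3.3 percentage points per complete responder among 30 evaluable subjects, given one integer score per subject. The complete share in this trial is unknown, and the loss also depends on how the three evaluators' scores are combined, which the plan does not say for pigment. The mean PCS would move by 0 to 0.15 points at the planning figures, given the assumed grades 1–3 of Section 9.1. The sample size and its power statement are sound on this point. It should be fixed before scoring, but it does not threaten the trial.

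**What to change.** Before any photograph is scored:

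1. Use one scale throughout. Appendix A (1–5) is preferable because Sections 19.1 to 19.3 already point to it or use its grades; correct Section 9.1 to match. A 0–4 scale would also be consistent, but Appendix A and the top score and grades in Sections 19.2 and 19.3 would then have to change.
2. In the synopsis and Section 17.3, define a responder as at least 50% clearance with all higher grades included, that is PCS ≥ 3 on Appendix A. This also settles the boundary, since score 3 begins at exactly 50% while the gloss says more than 50%.
3. State both Section 19.2 hypotheses for good, excellent or complete improvement.
4. Use the name PCS in Section 19.2 and in the Section 30 list.

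The cost is wording in the synopsis, Sections 9.1, 17.3 and 19.2 and the Section 30 list, with no new data and no change in sample size.

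Two matters remain open after this change and need their own correction: how three pigment scores become one, and what a difference from Baseline means for a score that already rates improvement from Baseline.
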